## 1.0 Introduction

Over half of breast cancer survivors experience sexual concerns resulting from physical changes due to breast surgery, chemotherapy, and hormonal therapies; emotional changes; and relationship difficulties. In contrast with many aspects of quality of life (QOL) that tend to improve over time for breast cancer survivors, sexual concerns often persist for years. As a result, many breast cancer survivors and their partners may wish to resume a satisfying intimate relationship after treatment ends but encounter difficulties in doing so. Sexual concerns often go unaddressed, can lead to clinically significant psychological distress, and have a negative impact on survivors' relationships and quality of life. Thus, addressing sexual concerns and improving sexual function is of critical importance to the long-term adjustment of these survivors. Given the central role of the intimate relationship in breast cancer survivors' sexual experiences, a couple-based intervention that systematically involves the partner may be the most effective approach for addressing these concerns and improving function. Yet to date, there have been no RCTs testing the efficacy of a couple-based intervention targeting sexual function for breast cancer survivors.

## 2.0 Objectives

The objective of the proposed study is to evaluate the IE intervention in 120 female early stage breast cancer survivors reporting sexual concerns and their intimate partners. Couples will be randomized 1:1 to receive either the IE intervention (Intimacy Enhancement; IE) or to a previously tested attention control condition (Living Healthy Together; LHT). We will evaluate IE effects on a range of patient and partner sexual, relationship, and psychological outcomes and examine treatment mediators and moderators.

### 2.1 Specific Aims

**Specific Aim 1 (Primary Aim):** To evaluate whether the IE intervention will lead to a significantly greater increase in patient sexual function from pre-treatment to post-treatment and 3- and 6-month follow-ups compared to the LHT condition.

**Specific Aim 2 (Secondary Aim):** To evaluate whether the IE intervention will lead to significantly greater improvements in (a) partner sexual function and (b) patient and partner relationship intimacy and quality and psychological distress from pre-treatment to post-treatment and at 3- and 6-month follow-ups, compared to the LHT condition.

**Specific Aim 3 (Secondary Aim):** To evaluate whether increases from pre- to post-treatment in patient sexual communication and self-efficacy for coping with sexual concerns mediate the beneficial effects of the IE intervention on patient sexual function at 3- and 6-month follow-ups.

**Exploratory Aim 1:** To explore whether age ( $\leq 45$  versus  $> 45$  at diagnosis) and race/ethnicity (White versus non-White) moderate intervention effects on the primary outcome of patient sexual function.

**Exploratory Aim 2:** To identify participation barriers and intervention preferences of breast cancer survivors who choose not to participate in the Intimacy Enhancement study.

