### **4.2.3 Self Report Measures**

#### **4.2.3.1 Primary Outcome Measure (Primary Aim)**

Patient Sexual Function. Patients will complete the primary outcome measure, i.e., the 19-item Female Sexual Function Index (FSFI), at all four time points (T1-T4). The FSFI is a widely used sexual function measure with established validity in breast cancer. The FSFI is an optimal primary outcome measure because it is comprehensive and multi-dimensional, in that it assesses biological, psychological, and social dimensions of women's sexual experiences including desire, arousal, pain, and satisfaction with sexual relationship, all of which may change due to participation in the IE intervention. Further, in our breast cancer pilot trial, we found a very large effect size for patient sexual function (Cohen's  $d=1.30$ ). The total score will be used as the primary endpoint as it reflects women's overall sexual

function. In addition, we will conduct separate models for each sexual function domain as a supplemental analysis to clarify which domains of sexual function may be driving any effects on overall function. FSFI scores are sensitive to increases in response to participation in behavioral (non-medical) intervention trials in women with cancer up to the proposed 6-month time point.

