#### **4.2.3.3 Mediators (Aim 3)**

Patient and Partner Sexual Communication. Sexual communication is assessed through a brief 6-item version of the Dyadic Sexual Communication Scale (DSCS). The DSCS assesses the quality of communication in a couple's intimate relationship specifically related to sex that has been used successfully in cancer studies. The original scale has 13 items. However, with the aim of reducing participant burden we conducted several analyses including item response curves and correlational analyses to determine whether a shorter version of the DSCS would be valid without losing information. These analyses suggested items 2, 3, 4, 10, 11, and 12 provided 95% correlation with the larger scale. Thus we will use these items in place of the larger scale. Patient and Partner Self-Efficacy for Coping with Sexual Concerns. Self-efficacy for coping with sexual concerns is assessed through three items measuring participants' confidence in their ability to deal effectively with sexual concerns, communicate effectively about sexual concerns, and enjoy sexual intimacy despite physical limitations. These items were developed using standard methods for constructing self-efficacy scales according to social cognitive theory for the IE colorectal cancer study and have high internal consistency as a single scale (Cronbach's alpha=.91). Items use a 0-10 rating scale and reference the past week.

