#### 4.3 Overview of Randomization and Intervention Conditions

Couples will be randomized with an allocation ratio of 1:1 to either the IE or the Educational Control (Living Healthy Together) condition with stratification by age at diagnosis ( $\leq 45$  vs.  $> 45$ ) using the age obtained from the medical record (or by the patient during screening, if age at diagnosis is not available in the medical record). The statistician ([name]) will generate the randomization sequences using an automated randomization procedure in REDCap that limits prediction of allocation and protects masking of allocations. Randomization in blocks of four will guarantee that after every four assignments the study arms will have equal numbers. Separate randomization tables will be used for FCCC, Duke, and community participants to minimize the potential for unequal randomization by site.

Randomization will occur once both members of the couple have consented, completed baseline surveys, and are scheduled for their first intervention session. Randomization will occur centrally at the primary site by a staff member uninvolved in recruitment (to reduce the potential for bias in randomizing participants onto certain conditions). Once randomized, the couple will be sent sealed study materials along with the instructions to leave the envelopes sealed until they “meet” with their interventionist for session 1. It is important to keep the study condition a secret from participants until Session 1 to reduce the chances for unequal drop-out prior to Session 1, which could occur if patients/partners are more motivated to attend sessions in one study group as opposed to the other.

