### **13.5 Statistical Analyses for Aim 3 (Secondary; Mediators of IE Effects on Patient Sexual Function)**

To evaluate whether changes in either sexual communication and/or in self-efficacy for coping with sexual concerns mediate treatment effects on sexual function for patients in the IE condition at 3- and 6-month follow-up, we will use the causal inference framework for mediation described by VanderWeele and others to evaluate whether change (increase) in the mediator variable from pre-treatment to post-treatment mediates improvement (increase) in patient sexual function. Initial models will look for mediation at 3-month follow-up; if evidence of mediation is found, we will also test mediation models which include 6-month follow-up. Effects will be estimated via structural equation modeling, and covariates (age, race, etc.) will be included to account for possible mediator/outcome confounding. Separate models will be fit for the two proposed mediators.

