
**Quality Assurance Procedures for Other Study Aspects.** First, to promote transparency, the trial will be registered on clinicaltrials.gov and a protocol paper will be published. Second, we have designed standardized procedures for every aspect of study administration, from the candidate screening process to administration of the study conditions. Third, all outcome measures have demonstrated excellent psychometric properties and have prior research supporting their appropriateness in the study population and sensitivity to interventions. Fourth, REDCap, a secure web-based application, will be

used for data collection and for randomization, with an automated procedure that limits prediction of allocation and protects masking of allocations. Finally, to facilitate unbiased data collection and analysis the following steps are taken: 1) the data analyst will conduct outcome data analyses on data in which study condition is masked; 2) outcome data collection is completed in an automated fashion using REDCap, minimizing the need for contact with participants to collect study data; 3) if needed, manual data collection will be completed by study staff for whom the participant's assignment is masked to the extent possible. On an annual basis, adverse events will be reviewed across study conditions. During the annual review of adverse events, the presence of significant between-group differences could potentially warrant unmasking of the study conditions by the study biostatistician. As with most behavioral interventions, study interventionists, intervention supervisors (site PI's), and participants are not blind to study condition.

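### Aim 3 takes mediator and outcome from the same unblinded patient's questionnaires and leaves the partner's communication rating unused, so reporting tendencies that differ between women can look like mediation

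*Combined protocol and SAP*

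**What the plan says.** Section 2.1 (Specific Aim 3) tests whether "increases from pre- to post-treatment in patient sexual communication and self-efficacy for coping with sexual concerns mediate" the benefit of IE on patient sexual function at 3 and 6 months. Hypothesis 3 in section 2.2 is worded to match. The outcome is the patient's own Female Sexual Function Index (FSFI) total (section 4.2.3.1). The mediators are her Dyadic Sexual Communication Scale (DSCS) and self-efficacy scores, taken as change from baseline to post-treatment.

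Section 4.2.3.3 shows that both members of the couple complete the communication scale: "Patient and Partner Sexual Communication. Sexual communication is assessed through a brief 6-item version". Table 2 schedules it at baseline and post-treatment, without the asterisk that marks patient-only measures.

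Section 13.5 plans structural equation models within a causal mediation framework, with demographic and similar covariates against mediator-outcome confounding. It adds that "Separate models will be fit for the two proposed mediators". It names no sensitivity analysis, and no part of section 13 uses the partner's DSCS.

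Section 16.1 states that "study interventionists, intervention supervisors (site PI's), and participants are not blind to study condition". Section 4.3 adds: "It is important to keep the study condition a secret from participants until Session 1". Baseline is therefore answered before the arm is known, and post-treatment after.

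**The concern.** Randomization protects the path from treatment to mediator but not the path from mediator to outcome. If one woman supplies both measurements, anything that makes her rate both more or less favourably adds to their association within arm. Age and race do not remove that.

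The stake is what Aim 3 may conclude. It is a prespecified secondary aim meant to explain how IE works. With one reporter at both ends of the path, a finding that communication mediates the effect is hard to tell from correlated reporting. For communication, a second informant on the same couple-level construct is already being collected.

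**Working it through.** **1. The plan's own figure.** Section 13.8 gives power for Aim 1 only. 120 × 0.76 = 91.2, stated as 92 couples, so 46 per arm. The standard error is 8.2 × √(2/46) = 1.71, and 5/1.71 = 2.92. A two-sided 5% t-test then has 82.5% power against 82% stated, so the figure is reproduced. No power is given for Aim 3; I use 46 per arm below.

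**2. Do partners complete the DSCS?** The partner item totals in Table 2 say so (DSCS = 6; male partner, IIEF = 15):
- Baseline: 15+17+7+9+7+**6**+7+9+15+2+6+19 = 119, as stated.
- Post-treatment: 15+17+7+9+7+**6**+7+1+6+3+4+8+14+5 = 109, as stated.
- 3 months, DSCS not scheduled: 15+17+7+9+7+1+5 = 61, as stated.

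**3. A reporting tendency present at all visits.** The documents give no inputs, so all of these are assumptions:
- Communication has no true effect on sexual function.
- IE raises the mediator by 0.6 SD. The total effect is 5/8.2 = 0.61 SD.
- A patient-specific reporting component is shared by both measures. It takes share s of each variance (each set to 1) and correlates ρ between any two of baseline, post-treatment and follow-up.
- 60% of the remaining variance is stable over time within each measure.
- The mediator is the change D. The outcome is adjusted for arm and baseline FSFI. Section 13.5 does not state the baseline adjustment; I take it from section 13.2.

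Within arm, let κ = sρ + 0.6(1−s) be the covariance of each measure between visits. Then Var(D) = 2(1−κ). The covariance of D with follow-up FSFI is sρ − sρ = 0, and with baseline FSFI it is −c, where c = s(1−ρ). The false mediator-outcome coefficient is b = cκ/(Var(D) − c²), and the false proportion mediated is 0.6b/0.61.

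For the joint test, the first path has z = 0.6/√(Var(D) × 2/46). The second has partial correlation r = b√((Var(D) − c²)/(1 − κ²)) and t ≈ r√88/√(1 − r²).

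| s, ρ | κ | Var(D) | c | b | False proportion mediated | Chance path 1 significant | Chance path 2 significant | Both |
|---|---|---|---|---|---|---|---|---|
| 0.2, 0.7 | 0.62 | 0.76 | 0.06 | 0.049 | 5% | 0.91 (z = 3.30) | 0.08 (t = 0.51) | 7% |
| 0.4, 0.7 | 0.64 | 0.72 | 0.12 | 0.109 | 11% | 0.92 (z = 3.39) | 0.20 (t = 1.12) | 18% |
| 0.4, 0.5 | 0.56 | 0.88 | 0.20 | 0.133 | 13% | 0.87 (z = 3.07) | 0.29 (t = 1.40) | 25% |

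Simulation over the grid agrees: 7-25% false mediation and 5-13% falsely mediated. A woman who happens to report low at baseline shows a larger rise in the DSCS. Her baseline FSFI also understates her level, so her follow-up FSFI exceeds its prediction. A more stable tendency cancels more fully in the change, so higher ρ lowers the bias.

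Without carry-over to follow-up, the FSFI covariance at s = 0.4 falls from 0.56 to 0.6 × 0.6 = 0.36. With ρ = 0.5, b then falls from 0.133 to 0.20 × 0.36/0.84 = 0.086.

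**4. A shift that starts once the arm is known.** This is a separate simulation: 46 per arm, a true communication gain of 0.5 SD with no effect on sexual function, and an IE-only reporting shift averaging 0.5 SD. False mediation with the patient-rated mediator was:
- identical shift in every IE woman: 5.5%;
- shift varying between women with SD 0.5: 15%; with SD 1.0: 72%;
- SD 0.5 plus a response style worth 20% of outcome variance, not cancelled by baseline: 55%, falling to 20% if half carries over to follow-up and to 4% if none does.

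With a partner rating free of her shift, the rate was 2-3% throughout. If the partner carries half her shift, it was 3-26% (7% where the patient-rated figure is 55%).

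**The case against.** A reader might infer three stronger things, none of which the documents support.

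- **That lack of blinding alone creates false mediation.** A shift common to all IE women raises the treatment-to-mediator path and the total effect, but not the within-arm association (5.5% above). The 7-25% contains no arm-related shift at all.
- **That the error rate is 11-61%.** That follows from using the post-treatment rating alone. The within-arm correlation is then share × ρ, from 0.2 × 0.5 = 0.10 to 0.4 × 0.7 = 0.28, and the false proportion mediated is 10-28%. But Aim 3 uses pre-to-post change, and the primary model adjusts for baseline FSFI, so part of a persistent tendency cancels.
- **That mediation should be claimed only if the partner-based estimate points the same way.** With no true effect, that sign is close to a coin toss. Such a rule still declares false mediation in about 10-34% of trials on post-treatment scores and 5-14% on change scores. It could also suppress a true patient-level mechanism.

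The plan also has partial safeguards: a control matched for time and attention (section 16.1), credibility compared between arms (section 16.2), outcomes 3 and 6 months after the mediator, and covariate adjustment. These lessen the risk but do not separate shared reporting from mediation.

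Two objections to the partner model stand. The partner attends the sessions and is also unblinded. The partner's view is also not identical to hers, so a weak partner-based result may only reflect disagreement within the couple.

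**Conclusion.** The plan contains no contradiction or error here, but it has a real gap in a secondary aim. Mediator and outcome share one unblinded reporter, the only stated protection is covariates, and the partner's DSCS is assigned to no analysis. Under the assumptions in step 3, false mediation by a joint test is roughly 7-25% against a nominal 5% or less. It is lower if the tendency does not carry over to 3 or 6 months.

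The range depends wholly on the assumed 20-40% shares, correlations of 0.5-0.7 and 60% stability, so it shows plausibility and is not an estimate for this trial. The higher figures in step 4 need a widely varying shift, or a response style that baseline does not cancel, together with full carry-over; I do not rest the point on them. Aim 1 and its power are unaffected.

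**What to change.** In section 13.5, before outcome data are analysed:

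1. For sexual communication, prespecify a sensitivity mediation model with the partner-reported DSCS change (baseline to post-treatment) as mediator and patient FSFI as outcome, adjusted for baseline FSFI and baseline mediator.
2. Report its indirect effect with a confidence interval beside the patient-based result. If the partner-based estimate does not support that result, describe it as possibly due to shared reporting. Do not make same-sign agreement a condition for claiming mediation.
3. For both mediators, add a sensitivity analysis for correlated mediator and outcome errors, showing how large the correlation must be to remove the indirect effect. Self-efficacy depends on this analysis, because the partner's score is the partner's own confidence and not a second rating of hers.

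The cost is SAP wording and a few extra models on data already collected, with no added visits or items. The downside is that the partner is unblinded and present at the sessions, and weak agreement between partners can shrink the partner-based estimate. The change reduces the ambiguity but does not remove it.

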### 2.2 Research Hypotheses

**Hypothesis 1:** The IE intervention will lead to an increase in patient sexual function from pre-treatment to post-treatment and 3- and 6-month follow-ups compared to the LHT condition.

**Hypothesis 2:** The IE intervention will lead to significantly greater improvements in partner sexual function, patient and partner relationship intimacy and quality, and psychological distress from pre-treatment to post-treatment and at 3- and 6-month follow-ups, compared to the LHT condition.

**Hypothesis 3:** Increases from pre- to post-treatment in patient sexual communication and self-efficacy for coping with sexual concerns will mediate the beneficial effects of the IE intervention on patient sexual function at 3- and 6-month follow-ups.

### 3.0 Background/Rationale

Nearly one third of all new cancer diagnoses in women in 2016 were for breast cancer. For the majority of women (61%) diagnosed with localized breast cancer, the 5-year survival rate is 99%. Advances in detection and treatment improve survival for breast cancer, yet these life-extending treatments often come at a considerable cost for survivors' intimate relationships. As many as 70% of breast cancer survivors report experiencing sexual concerns that impact their sexual function. Common concerns include those that are biological (e.g., vaginal dryness, pain during sex), psychological (e.g., loss of sexual desire), or social in nature (e.g., reduced sexual activity; see Table 1). Some of the most chronic and distressing sexual concerns for breast cancer survivors result from the estrogen suppression effects of chemotherapy and hormone therapy (e.g., aromatase inhibitors). Post-surgery body changes, including the loss of breast and nipple sensitivity, can interfere with sexual activity and impede women's sexual arousal, a key component of women's sexual function. Loss of sexual desire is one of the most common problems with sexual function for breast cancer survivors, and is among the most problematic because it can significantly disrupt women's intimate relationships. Yet, although breast cancer survivors' physical and emotional health tend to improve over time after treatment completion, problems with sexual function and related concerns tend to persist and can therefore lead to long-term negative consequences for the intimate relationship, and psychological distress. Further, breast cancer survivors with more severe sexual concerns report higher disease interference and worse QOL, suggesting the critical importance of addressing such concerns.

In prior pilot studies in couples facing colorectal cancer, we demonstrated that a 4-session Intimacy Enhancement (IE) intervention delivered via telephone had positive effects on patient and partner sexual and relationship outcomes. The couple-based IE intervention includes education and training in cognitive and behavioral skills to cope with sexual concerns. It is grounded in social cognitive theory (e.g., emphasizes self-efficacy for coping with sexual concerns) and applies effective practices drawn from cognitive behavioral couple therapy (e.g., communication skills training) and sex therapy (e.g., sensate focus). With breast cancer survivors' input, we modified the IE intervention content to optimize relevance of the educational materials and adapt skills training and practice for this population. Preliminary results from a pilot trial in breast cancer survivors and their partners suggest this intervention is feasible and acceptable in a diverse sample, and shows promise in improving patients' sexual function and related patient and partner outcomes. However, a full-scale randomized controlled trial is needed to evaluate the IE intervention's efficacy, investigate mediators of treatment effects, and explore potential intervention moderators.

### 4.0 Study Design

#### 4.1 Recruitment methods

Number of subjects per year projected at FCCC	Total number of subjects at FCCC	Number of subjects nationally or internationally (if applicable)	Number of subjects at collaborating institutions (if applicable)
Up to: 60	Up to: 180	0	125

The human subjects in this entire project include approximately 120 breast cancer patients and 120 spouses or partners of breast cancer patients who will be asked to provide their time and personal

information as part of the intervention study, plus an additional estimated 35 to 40 patients who will complete the developmental survey (exploratory aim 2), for a total of approximately 280 participants. Participants will be recruited primarily from FCCC/Temple and Duke University Medical Center (DUMC). DUMC will serve as a separate recruitment site from FCCC and will operate under its own IRB. DUMC study staff will be supervised by the site Principal Investigator, [name]. Oversight of recruitment challenges and data collection will be done by FCCC.

Two key methods for recruitment were used successfully in our pilot trial at for site-based recruitment at FCCC and will be utilized again for the larger proposed trial. Potentially eligible candidates will be identified from each provider's clinic schedules and then the research assistant will query the provider as to the patient's eligibility. This pre-identification process involves pre-screening of patients using their medical records on major characteristics (e.g., disease stage, current treatment status, length of time since treatment, ECOG score) to reduce unnecessary burden of contacting patients who will not screen in or of contacting patients who may be ill. If the provider approves, a letter will be sent to a candidate summarizing the research study from the patient's provider including a phone number for the patient to call to indicate that she is not interested in pursuing the study further. Identification of patients may also occur through the tumor registry at FCCC, TUH, and DUMC and/or provider schedules (for patients who cannot be approached in clinic for any reason).

Temple patients will be identified either through [name] clinic schedule or the TUH cancer registry. The TUH cancer registry will include patient MRNs, marital status, diagnosis date, stage, and race/ethnicity, and will be provided to the study team by the manager of the registry. As with Fox Chase patients, eligible TUH patients will be identified through pre-screening of the electronic medical record. Recruiting staff will ask [name] permission to approach any eligible patients before contacting them.

Although patient data obtained through the registry are already limited based on disease type and stage, all patient records are checked prior to sending research invitation letters in case patients' medical conditions have changed, as in the case of disease recurrence or death.

In an effort to bolster recruitment and increase the diversity of the study sample, we will recruit simultaneously through our community partnership with Sista's Daughters, Inc. (SDI). Recruitment through SDI will primarily occur through attending community outreach events including workshops, cancer support groups, and health fairs. This model can be mutually beneficial in that the community members are able to obtain useful information on health and related topics, while bolstering community-based recruitment for the research project. [name] will plan special talks on relationships or sexual health in the context of cancer or other related topics, dependent on interest. Community-based recruitment efforts (i.e., eligibility screening and enrollment) will be conducted by FCCC staff, but medical eligibility will be determined by the patient's physician using a standard form.

Through our collaboration with [name] at the Cancer Support Community (CSC), we have the option of recruiting through CSC events and through email blasts sent to potentially eligible participants in the CSC Cancer Experience Registry, which as of the writing of the grant application, included 4,836 women diagnosed with non-metastatic breast cancer, of whom many report impact on their sexual lives. These recruitment methods will serve as methods of identifying potential candidates for the study; screening will proceed as for other community-based individuals, as reported below. The email blast will contain an attachment of a one-page informational handout (similar to the recruitment brochure, but in a format more suited to reading as an email attachment) and a REDCap link to a survey where patients who are opting in to be contacted about the study may provide their contact information. We may also post the flyer or informational material on the CSC website, online forums or

social media sites, and other CSC communications as appropriate, and in consultation with our CSC collaborators. These methods may also be utilized by our team in conjunction with other non-profit organizations that express interest in sharing information about the study.

In addition, we will also post study recruitment brochures or other advertisements in clinic and patient areas (e.g., education and resource room), and may also advertise through FCCC social media and through existing FCCC breast cancer-related events and newsletters.

